4.4.2. Microbiological

- To assess time to culture conversion, cure, and rates of clinical TB relapse
- To determine the prevalence of HR-TB stratified by geographic location
- To determine the prevalence of pre-XDR and XDR-TB using phenotypic DST to bedaquiline, pretomanid and linezolid
- To determine the proportion of participants with bedaquiline and linezolid resistance warranting a switch from short-course treatment
- To assess the clinical utility of the TB Molecular Bacterial Load Assay (TB-MBLA) as a predictor of treatment outcome
- To assess the diagnostic and clinical performance of the test and triage approach by geographic location using whole genome sequencing (WGS) and Minimum Inhibitory Concentration (MIC) analysis
- To determine the phylogenetic structure and full drug resistance patterns of study samples, including bedaquiline, linezolid, levofloxacin and pretomanid

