7. STUDY ASSESSMENTS AND FOLLOW-UP

7.1. Schedule of evaluations

The sequence of study visits and procedure schedules are presented in tables 3 and 4 schedule of evaluations for cohort 1 and 2, respectively. These tables detail visit requirements for each in-person follow-up visit. Each follow-up visit will include collection of a sputum sample, a clinical examination and assessment for adverse drug reactions. Study staff will be trained to conduct study procedures in a standardised manner. Study specific standard operating procedures (SOPs) will guide this process.

Screening (Cohorts 1 and 2):

Screening will include the provision of introductory study information, assessment of eligibility criteria and obtaining written informed consent for screening procedures. Participants who meet the eligibility criteria will provide up to two sputum samples for currently available Nucleic Acid Amplification Tests for drug-resistance detection and Xpert XDR testing. For potential participants who do not meet the study eligibility criteria, the screening process will be discontinued when ineligibility is determined.

Evaluations for Cohort 1:

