Participants will be scheduled to undergo appropriate evaluation at baseline, during and after treatment. Study visits will occur at week 2, monthly for the duration of DR-TB treatment and 3-monthly following completion of treatment where allowable within the study's operational time frame. Participants on short-regimen will be seen for a maximum of 3 post-TB treatment visits, 3 months apart (Table 3). Active follow-up will occur for the duration of TB treatment and passively thereafter, for a maximum of 18 months after study enrolment. Participants who receive long treatment regimens will be actively followed-up for the duration of the intensive phase of treatment and passively thereafter to obtain an end-of-treatment outcome. Research-specific activities during follow-up include assessment of clinical and microbiological response to treatment, solicitation and reporting of adverse events and serious adverse events, administration of study specific questionnaires related to costs, acceptability and feasibility of the intervention. Passive follow-up will be conducted telephonically or through NTP registers to assess rates of relapse after TB treatment completion. Study related specimen collection will occur at baseline (enrolment) and at all follow-up visits. Baseline sputum samples will be collected for Xpert MTB/XDR testing, pDST, WGS, and TB-MBLA testing. Follow-up sputum samples will be collected for routine culture and susceptibility testing and sputum storage for batched TB-MBLA testing.

Evaluations for Cohort 2:

Participants will be referred to the NTP and will not undergo further active follow-up within the study (table 4). Treatment outcomes for these participants will be monitored passively through monthly telephonic monitoring or through routinely collected outcome data within the national TB program until 15 months after enrolment.

Table 3: Schedule of Evaluation for Drug-Resistant Tuberculosis participants in the TRiAD Study Cohort 1

Visit	Screening	Enrolment	24h after 1 st treatment dose	Treatment and Follow Up Period ^a											
				Week 2	Month 1	Month 2	Month 3	Month 4	Month 5	Month 6	Month 9	Month 12	Month 15	Month 18	
Time of visit															
Inclusion/Exclusion Criteria	X	X													
Informed Consent	X	X													
Storage informed consent ^g		X													
Sociodemographic Information		X													
Medical/treatment History ^b		X													
Clinical Exam ^c		X		X	X	X	X	X	X	X	X	X	X	X	X

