TB Symptom Profile	X	X		X	X	X	X	X	X	X	X	X	X	X	X
Peripheral Neuropathy Assessment		X		X	X	X	X	X	X	X	X	X	X*	X	
ECG monitoring		X		X	X	X	X	X	X	X	X	X	X	X	X
Chest X-Ray ^d		X						X			X		X		
Laboratory Safety Assessments ^e		X		X	X	X	X	X	X	X	X	X	X	X	X
Sputum Sampling ^f	X	X		X	X	X	X	X	X	X	X	X	X	X	X
Blood sampling (1x4ml EDTA Tube) ^h		X					X							X	

Spot Urine collection sample (approximately 30ml) ⁱ		X											
Self -collection urine sample (approximately 5L) ^j			X								X		
Participant Questionnaire ^k		X											
Solicited Adverse Events (AES)/SAE ^l			X	X	X	X	X	X	X	X			

Notes:

- a. **Treatment and follow-up:** Active follow-up will occur during TB treatment only, passive follow-up visits up to 18 months post-TB treatment, no specimen collection during passive follow-up. Visits for month 12 onwards applicable to participants who continue treatment for longer than 6 months only. Passive follow-up visits will collect AE's, SAE's, verification of survival and participant reported TB outcome information. These will be conducted telephonically
- b. **Medical History:** will include TB treatment history, HIV/Status and CD4 and Viral load Monitoring: If HIV status is unknown or reported negative in the absence of documentation, HIV test should be requested. CD4 and Viral load test to be conducted for all HIV-positive participants as per standard of care
- c. **Clinical Exam:** will include random blood glucose test, ophthalmic examination of visual acuity and colour vision assessment, pregnancy test will be conducted in women of child-bearing potential and peripheral neuropathy assessment
- d. **Chest X-Ray:** Will be conducted at screening visit, month 4 (South African standard of care) and thereafter at the request of the treating clinician if deemed necessary. In Nigeria, X-rays will be done at screening visit, month 4 and end of treatment
- e. **Laboratory Safety Assessments:** Haematology, full blood count, clinical chemistry and urinalysis - as per routine in-country standard of care
- f. **Sputum Sampling:** 1 sample will be collected at baseline/screening: for currently available Nucleic Acid Amplification Tests for drug-resistance detection, routine culture and Xpert XDR testing, *an additional sample will be requested if required*, 2 samples will be collected at enrolment: storage for TB-MBLA and WGS/MIC testing

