Not evaluated	A participant for whom no treatment outcome is assigned. (This includes cases “transferred out” to another treatment unit and whose treatment outcome is unknown)	A patient recorded in the register and who does not have the necessary recorded data to enable classification of any outcome
Treatment success	The sum of cured and treatment completed	Is sum of cured and treatment completed

Sustained treatment success (optional outcome)		A patient assessed at 6 months and at 12 months after successful TB treatment, who is alive and free of TB.
--	--	---

*For treatment failed, lack of conversion by the end of the intensive phase implies that the participant does not convert within the maximum duration of the intensive phase applied by the programme. If no maximum duration is defined, an 8-month cut-off is proposed. For regimens without a clear distinction between intensive and continuation phases, a cut-off 8 months after the start of treatment is suggested to determine when the criteria for *Cured*, *Treatment completed* and *Treatment failed* start to apply.

The terms “conversion” and “reversion” of culture results are defined as follows:

- **Conversion** (to negative): culture is considered to have converted to negative when two consecutive cultures taken at least 30 days apart are found to be negative. In such case, the specimen collection date of the first negative culture is used as the date of conversion.
- **Reversion** (to positive): culture is considered to have reverted to positive when after an initial conversion, two consecutive cultures taken at least 30 days apart are found to be positive.

“Recurrent TB” is defined as being either of the following circumstances after cure or completion of treatment:

- Two consecutive positive cultures, or
- One positive culture with clinical signs and symptoms or radiographic deterioration (an isolated positive smear or culture without clinical or radiographic deterioration after treatment completion provides insufficient evidence to define recurrent TB).

If genotyping is available, recurrent TB may be further classified as relapse, reinfection, or undetermined as defined below:

- **Relapse**: isolates of the recurrent episode share the same genotype pattern with isolates of the first episode of MDR-TB.
- **Reinfection**: isolates of the recurrent episode and isolates of the first episode of MDR-TB have different genotype patterns.

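### Recurrence is defined by positive culture, but Table 3 note a takes no specimens after treatment while section 7.1 and Table 5 do, so the secondary relapse rate would be incompletely ascertained under note a

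*Protocol*

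**What the plan says.** **The objective.** Section 4.4.2 lists "To assess time to culture conversion, cure, and rates of clinical TB relapse". The outcome list in section 4.5 has no entry for relapse or recurrence.

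**The definition.** Section 9.3 gives two ways to qualify as recurrent TB after cure or completion: "Two consecutive positive cultures, or" the alternative, "One positive culture with clinical signs and symptoms or radiographic deterioration". An isolated positive result without deterioration is expressly insufficient. Where genotyping is available, a recurrence may then be labelled relapse ("isolates of the recurrent episode share the same genotype pattern with isolates of the first episode of MDR-TB"), reinfection or undetermined.

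**The data source, first account.** Table 3 note a confines active follow-up to the treatment period and describes what comes afterwards as passive contacts by telephone. These collect adverse events, survival and the participant's own report of TB outcome, with "no specimen collection during passive follow-up". It also limits the visits from month 12 to participants treated for more than 6 months. The cohort 1 text of section 7.1 agrees on the source: "Passive follow-up will be conducted telephonically or through NTP registers to assess rates of relapse after TB treatment completion".

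**The data source, second account.** The same section opens with "Each follow-up visit will include collection of a sputum sample". Its cohort 1 text adds "Study related specimen collection will occur at baseline (enrolment) and at all follow-up visits", having just provided for 3-monthly visits after treatment, up to 3 for short regimens, as far as the study's time frame allows. The Table 3 sputum row is marked through month 18. Table 5 lists sputum and culture at every visit after screening and refers to positive cultures obtained after treatment.

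**The concern.** An outcome defined by culture needs a culture. One set of instructions provides it after treatment and the other removes it, and both sit in section 7.1 and its own table. A site cannot tell which to follow, and sites that choose differently will ascertain recurrence differently.

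What is at stake is the secondary relapse objective. For the short all-oral regimens under study, recurrence after treatment is the natural check on whether a favourable outcome lasts. If no specimen is taken, a participant with returning disease who is not cultured elsewhere cannot meet the section 9.3 definition and is counted as free of recurrence. An analysis plan cannot repair this later, because sputum that was not collected cannot be recovered.

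**Working it through.** The protocol states no expected relapse rate, precision or power, so there is no figure to reproduce. The check is a side-by-side reading and a count of visits.

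**Step 1: what section 9.3 needs.** At least one positive culture after treatment for any recurrence, and two if there is no clinical or radiographic deterioration. To call it relapse or reinfection, an isolate from the recurrent episode and one from the first episode, both genotyped. Without genotyping, recurrence can still be declared and left undetermined.

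**Step 2: what each account supplies after treatment.**

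| Source | Contact after treatment | Specimens after treatment |
|---|---|---|
| 7.1, cohort 1 text | Participants seen, up to 3 visits, 3 months apart | At all follow-up visits |
| Table 3, sputum row | Columns through month 18 | Sputum marked |
| Table 5 | All visits after screening | Sputum and culture |
| Table 3 notes g and h | 6 months after completion, optional subset | Blood (note g also names urine) |
| Table 3 note a | Passive, telephonic | None |
| 7.1, relapse sentence | Telephone or programme registers | None mentioned |

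**Step 3: count for a 6-month regimen.**
- Section 7.1 text: treatment ends at month 6, so visits fall at 6 + 3 = 9, 6 + 6 = 12 and 6 + 9 = 15 months. Scheduled post-treatment cultures: up to 3.
- Note a: months 12 and later do not apply, which leaves month 9 as a passive contact without specimens. Scheduled post-treatment cultures: 0.

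**Step 4: the same count for a 9-month regimen.**
- Section 7.1 text: visits at 9 + 3 = 12, 9 + 6 = 15 and 9 + 9 = 18 months, again up to 3.
- Note a: treatment exceeded 6 months, so the later columns apply, but the contacts are passive and without specimens, again 0.

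**Step 5: consequence for the rate.** Let *r* be the true recurrence proportion and *c* the share of recurrences that the programme confirms by culture to the section 9.3 standard. Under note a the rate found is *r* × *c*. The documents give no value for *c*. It may lie anywhere from 0 to 1, and the rate is complete only if *c* = 1. No text requires a culture, retrieval of an isolate or genotyping through the telephone or register route.

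**Step 6: the genotype split.** Even if post-treatment sputum is taken, Table 5 makes storage of later positive cultures optional, and the isolates that section 7.2 describes for sequencing come from screening or enrolment. The relapse/reinfection split is therefore not secured under either account.

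**The case against.** **The conflict may be narrower than it looks.** Section 7.1 introduces the tables as covering in-person follow-up visits, and the sentence requiring sputum at each follow-up visit comes shortly afterwards. It can be read as excluding telephone contacts. Note a also restricts the columns from month 12, so the crosses in the sputum row could be meant for participants still on treatment. This stands in part: those two items are weaker evidence. It does not remove the conflict, because the cohort 1 text says that short-regimen participants will be seen after treatment and that specimens are taken at all follow-up visits, and Table 5 expects cultures after treatment.

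**Registers may hold cultures.** They are a named source, and routine care may culture patients with symptoms. This stands. A reader might infer that relapse cannot be measured at all; the documents support only incomplete ascertainment.

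**Genotyping is conditional.** Section 9.3 applies the split only if genotyping is available and provides an undetermined class, so lack of genotypes alone does not defeat the recurrence outcome. This stands too.

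**Four samples.** Counting the Table 3 columns at months 9, 12, 15 and 18 suggests four post-treatment samples after a 6-month regimen. Section 7.1 caps the visits at 3, and note a removes month 12 onwards.

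**Bias by country.** A reader might infer that under-counting differs between the three countries. No text describes post-treatment culture practice in any of them, so this is not supported.

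**Conclusion.** The point holds as an inconsistency in the post-treatment specimen rules, combined with an outcome definition that is not tied to its stated data source. Its size is up to 3 scheduled post-treatment cultures against 0 for a 6-month regimen. The upper figure is a ceiling, since section 7.1 makes those visits depend on the study's time frame.

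If note a governs, recurrence as defined in section 9.3 is found only where the programme happens to culture the patient. The rate is then incompletely ascertained and probably under-counted. That direction assumes that section 9.3 is applied strictly and that not every recurrence is cultured in routine care; the protocol lets neither assumption be checked. The documents do not allow the amount to be estimated.

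The reach is limited to a secondary objective that section 4.5 does not carry into the outcome list. The two primary endpoints and the sample size do not depend on it. It should be corrected, but it does not threaten the main result.

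**What to change.** Reconcile note a with section 7.1, the Table 3 sputum row and Table 5, and state in section 9.3 which data decide recurrence. There are two workable routes.

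- **(a) Keep note a.** Redefine the outcome as programme-recorded or participant-reported recurrence. Drop the relapse/reinfection split or report those cases as undetermined, and report the share of participants with any post-treatment culture so that readers can judge completeness. Align the section 7.1 specimen sentences, the sputum row and Table 5. Cost: wording only. The result is a weaker outcome, honestly labelled.
- **(b) Keep post-treatment sputum.** Revise three parts of note a together: the specimen clause, the statement that contacts are by telephone, and the restriction from month 12. All must match the up to 3 in-person visits in section 7.1. Deleting the specimen clause alone would not do, because contacts would still be telephonic and month 12 onwards would still not apply after a 6-month regimen. If the genotype split is kept, make storage of recurrence isolates mandatory and provide for genotyping them. Cost: a commitment to those in-person visits and cultures, plus the storage and genotyping.

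Under either route, say how the clinical TB relapse named in section 4.4.2 relates to the section 9.3 terms and add the outcome to section 4.5.

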7.2. General Mycobacteriology

The following bacteriological tests will be performed at the local reference laboratory as per standard practice: smear, culture, diagnostic LPAs and pDST to BDQ and LZD in pre-XDR TB participants. At each visit, one early morning sputum sample will be tested for acid-fast bacilli (AFB) smear and culture. Study specific procedures assays will be carried out according to procedures described in the study laboratory manual. Sub-cultures will be shipped to Tuberculosis Supranational Reference Laboratory, San Raffaele Scientific Institute (OSR) for specialized tests such as MIC and WGS.

Table 5: Overview of microbiologic assessments performed after each visit

Visit	Sample Type	Microbiologic Assessments	
		Routine Testing	Study Intervention
Screening	< 2x Sputum samples	
 Direct microscopy for AFB; currently available Nucleic Acid Amplification Tests for drug-resistance detection changes, Hain Assay MTBDRplus and MTBDRs/ Culture for the presence/absence of M.tb Phenotypic DST to bedaquiline and linezolid 	
 GeneXpert XDR test¹
Enrolment	Sputum X2		
 Culture for presence/absence of M.tb Sub-culture for storage and shipment for MIC and WGS³ Sputum collection for TB-MBLA processing ²
All visits post screening	Sputum X2	
 Culture for the presence/absence of M.tb 	
 Sputum collection for TB-MBLA processing ² Any culture positive sample obtained during or after treatment will be stored at site level (optional)

Notes:

¹Xpert XDR testing: will be conducted on sputum sample collected at the screening visit following initial TB diagnosis by currently available Nucleic Acid Amplification Tests for drug-resistance detection changes. The Xpert MTB/XDR assay will be conducted in real-time to evaluate INH and second-line resistance and recommend the appropriate treatment regimen. This test will be conducted once off at the initial visit.

²TB-MBLA testing: the test will be conducted on stored sputum samples. The test will be conducted using LifeArc TB-MBLA test kits. This assay will be conducted to assess the clinical utility of the assay, not for clinical management. It is a reverse transcription quantitative polymerase chain reaction (RT-qPCR) assay that uses 16S-rRNA as a marker to detect and quantify the load of viable *M.tb* bacteria in a participant's sputum sample. The process starts with RNA isolation from *M.tb* bacteria, followed by RT-qPCR to quantify the RNA, then conversion of the RT-qPCR output (cycle threshold [CT] values) into bacterial load values (estimated colony forming units per millilitre [eCFU/ml]) using a standard curve.

³Culture for storage, MIC and WGS: Isolates will be cultured from sputum samples collected at the screening/enrolment visit using the BD BACTEC MGIT 960 culture system at National Reference TB Laboratory. Cultured isolates will be stored at -80 degrees Celsius for further processing. 70% of clinical isolates will be sent to the study reference laboratory; OSR. OSR will perform quality assurance assessments of the Xpert MTB/XDR cartridge to be tested. The drug patterns of resistant strains detected with the XDR assay will be fully characterized by OSR. In parallel, OSR will populate and develop a catalogue of resistance of the sites, complemented by MIC testing, and seek to identify resistance markers to guide future diagnosis and treatment decisions. WGS testing will be conducted on 70% of total samples from participants with RR-TB and HR-TB enrolled from all sites in cohort 1 and 2, respectively. MIC testing for full phenotypic DST will be prioritized on a subset of 480 samples maximum, including strains with unknown mutation patterns and/or from participants failing the proposed regimen. The accuracy of Xpert MTB/XDR test results for drug resistance prediction will be assessed and quality controlled by WGS analysis. One aliquot of viable isolates from study samples will be referred from sites to OSR, arranging one shipment in year 1 and two shipments per year in the years 2, 3, 4.

7.3. Cost effectiveness and acceptability analysis

7.3.1 Cost effectiveness

Through cost-effectiveness analyses we will determine the incremental cost per DALY averted from combined currently available Nucleic Acid Amplification Tests for drug-resistance detection and Xpert/XDR implementation, followed by an all-oral, shorter treatment regimen compared to the conventional standard of care for both DR-TB patients. Cost data on diagnostic and treatment algorithms will be collected through an ingredient approach from a societal perspective, including both health system and patient costs. Both provider and patient cost data will be collected empirically from all nine sites once the optimal implementation scenarios have been generated. Gaps in provider costs captured in previous costing studies will be collected through semi-structured interviews of key informants and document review. Patient costs of cohorts 1 and 2 participants will be collected via questionnaire by trained data collectors in tandem with select parent study follow-up visits.

The primary outputs will include incremental cost per DALY averted and incremental cost per day of treatment delay averted compared with historical controls. These outcomes are assessed from the societal perspective and reported from each of the societal, provider, and patient perspectives. The cost-effectiveness comparison between the intervention and the standard of care will be modelled using primary data from the parent study, primary cost data

from providers and patients from all five trial sites, secondary data concerning national population characteristics and standard of care outcomes, as well as expert opinion, where necessary. The time frame of the model-based analysis will be from initial diagnosis to end of life. Deterministic and probabilistic sensitivity analyses will be conducted on model parameters and methodological assumptions.

